10. SAFETY AND TOLERABILITY ANALYSIS

The safety analysis will be run on the Safety Population. The analysis of safety assessments in this study will include summaries of the following safety and tolerability data collected for each participant:

- Adverse Events
- Clinical Laboratory Investigations
- C-SSRS
- Vital Signs
- Visual Examinations of Oral Cavity
- BDI-II

Summaries of continuous parameters will include raw values and change from baseline, as appropriate. Listings of safety data will also be presented.

Analyses in this Section 10 will be based on data collected in Study TNX-CY-P306. Long-term safety analyses that span subject data from TNX-CY-P301, TNX-CY-P303, and TNX-CY-P306 are addressed in Section 12.

10.1 Adverse Events

All AEs will be coded using MedDRA, version 19.0.

Newly emergent adverse events (NEAEs) are defined as any new AE that started after the patient's first dose of study drug in Study TNX-CY-P306, or any unresolved AE first reported in Study TNX-CY-P301 or Study TNX-CY-P303 that exhibited an increase in severity, frequency or relationship after the patient's participation in Study TNX-CY-P306 had begun. For clarity, adverse events are classified as NEAEs based on a negative response to the CRF question "Did the AE start prior to the first dose?".

An AE summary table will be presented for the following:

• NEAEs by severity

Protocol: TNX-CY-P306 Page 21 of 36

Final v1.0

• NEAEs leading to study drug discontinuation

- NEAEs by relationship
- SAEs
- Oral Cavity NEAEs

Summaries of incidence rates (frequencies and percentages) of individual AEs by MedDRA SOC and preferred term will be prepared. Such summaries will be displayed for all NEAEs, NEAEs by maximum severity, NEAEs by strongest relationship to study drug, and oral cavity NEAEs. Incidence of oral cavity NEAEs will be presented by category and preferred term, rather than SOC and preferred term.

Each participant will be counted only once within each summation level (SOC; preferred term). If a participant experiences more than one NEAE within each summation level only, the NEAE with the strongest relationship or the maximum severity, as appropriate, will be included in the summaries of relationship and severity.

Oral cavity adverse events will be defined by a custom MedDRA query (CMQ). These events will be further divided into 4 categories, as follows: 1) Sensory 2) Discomfort 3) Irritation/inflammation and 4) Lesions. Each category will be defined by a CMQ.

Additionally, a summary of the Oral Cavity AE characteristics will be presented; this includes information such as temporal proximity to the dose, duration and whether the AE was present the following morning. For purposes of this summary, only oral cavity NEAEs with the response "Yes" to the CRF question "Is AE in oral cavity"? will be included.

NEAEs pertaining to abuse potential will be reported by SOC and preferred term, and displayed in tabular format. Terms to be included may be found in Appendix 3.

In the AE data listings, all AEs collected in study TNX-CY-P306 will be displayed. AEs that are newly-emergent will be flagged.

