# 11. DEFINITIONS, RECORDING, AND REPORTING OF ADVERSE EVENTS AND PREGNANCY

## 11.1. Definition of Adverse Events

According to International Council on Harmonisation (ICH) guidance E2A, Clinical Safety Data Management: Definitions and Standards for Expedited Reporting, an AE is any untoward medical occurrence in a patient or clinical investigation patient administered a pharmaceutical product and which is not necessarily required to have a causal relationship with this treatment. An AE can therefore be any unfavorable and unintended sign (including an abnormal laboratory finding, for example), symptom, or disease temporally associated with the use of a medicinal product, whether or not considered related to the medicinal product.

A newly-emergent adverse event (NEAE) is defined as any new AE that starts after the patient's baseline visit for P306, or any ongoing AE that was first reported during the lead-in study or 12-

week open-label extension study and which then exhibits an increase in severity, frequency or relationship after the patient's participation in P306 has begun. NEAEs and "All AEs" will be tallied by System Organ Class (SOC) and preferred terms. AEs that are ongoing at the time of the patient's baseline visit for P306 but which resolve, or persist without change in severity, frequency or relationship to study drug during the extension study, will be included in the tally of all AEs.

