10.1.1 Adverse Events Leading to Discontinuation of Study Drug

A summary of incidence rates (frequencies and percentages) of NEAEs leading to discontinuation of study drug by SOC and preferred term will be prepared for the Safety population.

A data listing of AEs leading to discontinuation of study drug will also be provided, displaying details of the event(s) captured on the CRF.

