10.1.2 Serious Adverse Events

A summary of incidence rates (frequencies and percentages) of newly-emergent SAEs by SOC and preferred term will be prepared for the Safety Population. A data listing of all SAEs will also be provided, displaying details of the event(s) captured on the CRF.

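### SAP 10.1 flags newly emergent AEs by a rule that covers only half of its own definition, and the protocol's all-AE tally is neither planned nor declared dropped

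*SAP*

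**What the plan says.** SAP 10.1 counts as an NEAE any new event that starts after the first P306 dose, and also "any unresolved AE first reported in Study TNX-CY-P301 or Study TNX-CY-P303 that exhibited an increase in severity, frequency or relationship" once P306 participation has begun. The sentence that follows, offered as clarification, says adverse events are "classified as NEAEs based on a negative response to the CRF question 'Did the AE start prior to the first dose". Protocol 11.1 has the same second limb: an ongoing event from an earlier study "which then exhibits an increase in severity, frequency or relationship" during P306 is newly emergent.

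The flag decides what enters the Section 10 incidence tables. On the tables by system organ class (SOC) and preferred term, SAP 10.1 says: "Such summaries will be displayed for all NEAEs, NEAEs by maximum severity, NEAEs by strongest relationship to study drug, and oral cavity NEAEs". The abuse-potential table is also limited to NEAEs. SAP 10.1.1 plans an incidence summary "of NEAEs leading to discontinuation of study drug by SOC and preferred term will be prepared", and SAP 10.1.2 one "of newly-emergent SAEs by SOC and preferred term will be prepared for the Safety Population". The AE listing shows every P306 event and marks the newly emergent ones.

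On tallies, Protocol 11.1 says: "NEAEs and 'All AEs' will be tallied by System Organ Class (SOC) and preferred terms". Events ongoing at P306 entry that resolve or do not change "will be included in the tally of all AEs". SAP Section 13 declares one change from plan, the numbering of study days.

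SAP 12.2 pools P301, P303 and P306. For patients on TNX-102 SL in P301, it treats events in the P303 or P306 database as treatment-emergent unless a collected start date precedes P301 treatment. It also keeps any event that was a treatment-emergent AE (TEAE) in the P301 report. For patients on placebo in P301, it takes only events newly emergent in P303 or P306.

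**The concern.** Every P306 patient comes from an earlier study, so events ongoing at entry are built into the design. The protocol synopsis and Protocol 9.1.5 have sites transcribe them. Such an event began before the first P306 dose, so its transcribed record is answered 'Yes' and is not flagged, whatever happens to it later. If it worsens, the definition says NEAE and the classification rule says not.

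Long-term safety is the primary objective, and Section 10 is where P306's own AE incidence is reported. One programmer working from the definition and another from the clarifying sentence could produce different tables from the same paragraph. The all-AE tally would have shown these events in a P306 table under either reading, and it is missing without being declared.

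**Working it through.** The plan states no figure on this point, so there is none to reproduce. The check sets the rules side by side.

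**Step 1. Definition against classification rule (SAP 10.1).**

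| Event in P306 | Two-limb definition | Clarifying rule |
|---|---|---|
| Starts after first P306 dose | NEAE | NEAE |
| Carried over, unchanged or resolves | Not NEAE | Not NEAE |
| Carried over, worsens, kept on its transcribed record | NEAE | Not NEAE |

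The rules disagree only in the last row.

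**Step 2. What Section 12.2 recovers.** Divide that last row by P301 arm and onset:

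| Type | P301 arm | Onset | Counted in 12.2? |
|---|---|---|---|
| a | TNX-102 SL | On or after P301 treatment start, or start date not collected | Yes |
| b | TNX-102 SL | Collected start before P301 treatment; was a P301 TEAE | Yes |
| c | TNX-102 SL | Collected start before P301 treatment; not a P301 TEAE | No |
| d | Placebo | Before first TNX-102 SL dose | No, if the CRF rule also sets 'newly-emergent' in 12.2 |
| e | Placebo | In P303, on TNX-102 SL | Yes |

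Types a, b and e are recovered; c is not, and d is conditional. These are categories of event, not frequencies, and say nothing about how many patients fall in each.

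**Step 3. Where the flag is used.** Section 10 plans seven incidence tables: all NEAEs, maximum severity, strongest relationship, oral cavity, abuse terms, leading to discontinuation, and newly emergent SAEs. All seven use the flag. So do four of the five lines in the AE overview; the exception is 'SAEs'. This counts where the flag is applied, not tables whose numbers would change.

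**Step 4. Size per patient.** A patient is missed in a row only if the event was ongoing at P306 entry, worsened in P306, was not re-entered as a new record, and the patient has no other NEAE in that row. Each such patient lowers the row by 1/N:

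- N = 200 (planned maximum, Protocol 6.2): 1/200 = 0.5 percentage point.
- N = 100 (assumed column size): 1/100 = 1.0 percentage point.
- N = 50 (assumed column size): 1/50 = 2.0 percentage points.

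The smaller columns are shown because SAP 7.1 generally tabulates by lead-in treatment group. The number of such patients cannot be obtained: the documents give no AE rates and no CRF completion rules.

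**Step 5. Tallies promised against tables planned.** Protocol 11.1 promises two tallies by SOC and preferred term, NEAEs and all AEs. SAP 10.1 to 10.1.2 plan such tables only for NEAEs and newly emergent SAEs. All P306 AEs appear only in a listing. Section 13 says nothing about this.

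**The case against.** The strongest reply is that undercounting is not shown. If sites open a new record whenever a carried-over event worsens, the answer becomes 'No', the event is flagged, and nothing is lost. That stands: zero is the lower bound. For some kinds of worsening the protocol makes the change itself recordable: PTSD symptoms that clearly worsen (10.4.1), a significant C-SSRS change (10.4.1.1), high ideation scores (10.4.1.2) and treatment-emergent clinically significant laboratory abnormalities (10.4.1.5). Inclusion criterion 4 also limits which events can be ongoing at entry. These narrow the gap, but none is a general rule for carried-over events.

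A second reply is that the clarifying sentence addresses only the first limb. It does not say so, and on that reading the SAP gives no derivation for the second.

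A third is that the tables meant to support the long-term safety profile are in Section 12, whose definitions may differ from Section 10's. This is largely right, and leaves only types c and d at risk there. But Section 12 pools three studies and does not replace P306's own NEAE tables.

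On the tally, Protocol 12 leaves the description of analyses to the SAP, and all events are listed. A listing is not a tally, and Section 13 is where the change should appear.

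Four stronger readings are tempting and not supported:

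- A reader might infer that the P306 safety tables are known to undercount. The documents do not show this. A missed event would still be in the AE listing without the flag, in the SAE or discontinuation listing if it qualifies, and in the overview 'SAEs' line if serious.
- A reader might infer from Step 3 that all seven tables are wrong. Using the flag is not the same as being changed by it.
- A reader might cite the synopsis as further proof that worsened carried-over events are NEAEs. It first says ongoing events are transcribed, then speaks of all other events that are newly reported or worsen. That also fits a worsening recorded separately, so the point rests on SAP 10.1 and Protocol 11.1.
- A reader might infer that only an all-AE table could show these events. Section 12.2 counts types a, b and e under either rule, and an all-AE table would mix worsened events with unchanged ones.

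**Conclusion.** The point holds as a contradiction between a definition and its stated implementation, with a separate undeclared departure from the protocol. An unresolved P301 or P303 event that worsens in P306 on its transcribed record is an NEAE by definition and is left out of the Section 10 NEAE tables by rule. The effect cannot be sized; it may be zero, and is 0.5 percentage point per missed patient per row at N = 200. In Section 12.2 the possible loss is confined to types c and d, and d depends on whether the CRF rule governs 'newly-emergent' there. This rests on the transcribed record being answered 'Yes' and on worsening not always being re-entered; the available documents settle neither in general. The missing all-AE tally does not depend on CRF practice. Both should be fixed, because the rule can give wrong counts for the primary objective and the correction is cheap.

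**What to change.** 1. Replace the clarifying sentence in SAP 10.1 with: NEAE = answer No, OR answer Yes with the AE unresolved at P306 entry and a recorded increase in severity, frequency or relationship after P306 participation began. This keeps the documents' own starting point for worsening.
2. State the data source: either a convention that worsening is entered as a new record, or a match to the P301 or P303 record. Declare in Section 13 any component the collected data cannot support. Frequency is a likely case, since Protocol 10.4.1 does not list it among the recorded AE fields.
3. Add the all-AE table by SOC and preferred term, or declare its omission in Section 13.
4. State in SAP 12.2 that 'newly-emergent' uses the full two-limb definition. This settles type d. Type c turns on the separate start-date exception, so 12.2 should also say whether such events are meant to stay out.

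The cost is SAP wording, a small derivation and one table or one Section 13 entry. NEAE counts may rise slightly. Recovery is limited to what the records hold: Protocol 10.4.1 lists severity and causality once per event, so a record never updated after entry shows no increase, and one merely re-rated at transcription could create a few false NEAEs. Data collection was probably over when the SAP was written, since it cites a 2023 source and the protocol estimated last completion in September 2019. The match should therefore be checked against the existing database before it is specified.

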#### Methodology:

This is an open-label, extension trial designed to evaluate safety of additional 40 to 52 weeks of TNX-102 SL 5.6 mg taken daily at bedtime for the treatment of PTSD. There are two possible "tracks" patients can use to enroll into this study:

Track A: patients that complete the double-blind lead-in HONOR study and complete *or are active (at the time of study discontinuation) in the* 12-week open-label extension study, P303, and received active drug in the 12-week double-blind lead-in study, P301/HONOR.

Track B: patients that are currently enrolled in the double-blind lead-in P301/HONOR study that has been discontinued due to results of an interim analysis *or are active (at the time of study discontinuation) in the* 12-week open-label extension study, P303, and received placebo in the 12-week double-blind lead-in study, P301/HONOR.

The study will consist of 5 or 6 in-clinic study visits, including Baseline Visit 1 (Day 0, which is anticipated to be the same visit as the last visit of the 12-week open-label extension study P303 for Track A patients), followed by in-clinic visits after 7, 16, 28 and 40 weeks of open-label treatment. Patients who are active in the 12-week double-blind lead-in study (P301/HONOR) at the time of enrollment to P306 will also have a 2-week phone check-in visit. All Track B patients will have 52 weeks of open-label treatment and a Visit 7. For patients enrolled from the discontinued double-blind lead-in study, P301/HONOR, the P306 Baseline Visit will occur in lieu of an early termination visit.

Patient safety parameters recorded at the final visit in the double-blind lead-in HONOR study (which is the baseline visit in the 12-week open-label extension study P303) can also be used as the baseline safety values for the P306 extension study for Track A patients. Patients will attend clinic visits at 7-, 9-, and 12-week intervals as indicated in the study visit schedule. Eligible patients who provide written informed consent will be provided with a supply of TNX-102 SL 2.8 mg tablets sufficient for

dosing until their next scheduled in-clinic study visit. At each clinic visit, patients will return their TNX-102 SL medication and will receive sufficient supplies to last them until the next scheduled visit. Patients will also have the option to have blood drawn for pharmacogenomic testing.

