## 6. INVESTIGATIONAL PLAN

## 6.1. Overall Study Design

This is a 40 to 52-week, multicenter, open-label extension study designed to establish long-term safety exposure and to examine the long-term effect with daily bedtime dosing of TNX-102 SL 5.6 mg (2 x 2.8mg tablets) in patients with PTSD. This study will be conducted at approximately 35 sites in the United States (US).

Patients who have either: (a) completed the double-blind lead-in study and complete, *or are active (at the time of study discontinuation)* in the 12-week open-label extension study, P303; or (b) are currently enrolled in the double-blind lead-in study (HONOR study) that has been discontinued due to results of an interim analysis, will be eligible. For Track A patients, this extension study consists of 5 in-clinic visits, including the Screening/Baseline visit and visits after 7, 16, 28 and 40 weeks of treatment (Visits 3-6). There will also be a telephone visit after two weeks of treatment (Visit 2) for patients enrolling from the double-blind lead-in study, P301/HONOR. The total treatment duration of this study will be 40 weeks for patients enrolled under Track A criteria, and 52 weeks for patients enrolled under Track B criteria. Therefore, the maximum total duration of continuous treatment with TNX-102 SL could be approximately 64 weeks for those patients assigned to TNX-102 SL in the lead-in HONOR study who then also completed the 12-week open-label extension study P303.

For patients enrolling from the open-label extension study, P303, there is no need to repeat assessments at Visit 1 for this study, if the patient enrolls and initiates study treatment within fourteen days of completing the 12-week open-label extension study P303. For patients who are active in the double-blind lead-in study, P301/HONOR, all Baseline procedures and assessments will be completed at Visit 1.

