3.2 Method of Treatment Assignment and Randomization

All patients will be assigned to TNX-102 SL, 5.6 mg regardless of which treatment arm they were randomized to in the lead-in study. No patients or site personnel will know what the prior treatment was in the double-blind lead-in study.

Throughout this document, when describing analyses performed by treatment group, this will refer to the treatment that the subject was randomized to in the double-blind lead-in study.

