7. GENERAL ISSUES FOR STATISTICAL ANALYSIS

7.1 General Statistical Methodology

Descriptive summaries will be provided where appropriate for each of the primary and secondary variables. In general, tables will summarize data by treatment group as defined in Section 3.2 and visit.

All tables will be completed for the Safety Population unless otherwise specified.

Continuous, quantitative, variable summaries will include the number of participants (N) with non-missing values, mean, standard deviation (SD), median, minimum, and maximum.

Categorical, qualitative, variable summaries will include the frequency and percentage of participants who are in the particular category. In general, the denominator for the percentage calculation will be based upon the total number of participants in the study population for the treatment group unless otherwise specified.

Unless otherwise noted, baseline values are defined as the last non-missing measurement prior to the first dose of open-label study drug in Study TNX-CY-P306. Change from baseline will be defined as the post-baseline visit value minus the baseline value.

ET participants will only be followed if required to monitor an on-going adverse event or other condition.

Participants are not supposed to change study sites; however, should this be necessary to allow a participant to continue in the study, participants will be analyzed under the site where they were initially enrolled.

Study day after first dose is defined as assessment date – first dose date +1. Dates prior to first dose are defined as assessment date – first dose date. Note that the protocol refers to "Day 0"; for the purposes of the datasets and analyses, this would appear as day 1.

All analyses will be performed using Statistical Analysis System (SAS®) Software version 9.4 or later.

Unless otherwise noted, 95% confidence intervals will be presented for statistical tests.

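### P306 adverse-event tables give only crude percentages although planned treatment is 40 weeks on one track and 52 on the other, so time at risk is mixed within a column and may differ between columns

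*SAP*

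**What the plan says.** **Statistic.** SAP 10.1: "Summaries of incidence rates (frequencies and percentages) of individual AEs by MedDRA SOC and preferred term will be prepared". A participant counts once per system organ class and once per preferred term. Sections 10.1.1 (discontinuations) and 10.1.2 (serious events) use the same statistic. By the general rule in SAP 7.1, "the denominator for the percentage calculation will be based upon the total number of participants in the study population for the treatment group". Section 10 contains no person-time, no common cut-off and no split by track.

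**Follow-up.** Protocol 6.1 sets planned treatment at "40 weeks for patients enrolled under Track A criteria, and 52 weeks for patients enrolled under Track B criteria"; SAP Section 3 repeats this.

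**Columns.** SAP 7.1: "In general, tables will summarize data by treatment group as defined in Section 3.2 and visit". SAP 3.2 explains that "when describing analyses performed by treatment group, this will refer to the treatment that the subject was randomized to in the double-blind lead-in study". SAP 10.1 itself names no columns. Protocol 12.1 and the synopsis plan safety as one group.

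**Track and lead-in arm.** In the protocol synopsis (Methodology), Track A patients came through P303 "and received active drug in the 12-week double-blind lead-in study, P301/HONOR". Track B takes patients still in P301, and patients active in P303 at discontinuation who had received placebo. Protocol 12.2 confirms that Track B also holds patients from the lead-in active arm. SAP Section 3 instead labels P303 entrants Track A and P301 entrants Track B, with no condition on arm.

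**Elsewhere.** SAP 12.2 plans tables by exposure interval with at-risk denominators. They pool TNX-102 SL across three studies, and time runs from the first active dose in any of them.

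**The concern.** Long-term safety is the primary objective. A percentage of everyone dosed has a clear meaning when all patients are observed for about the same time. Here planned observation differs by a factor of 52/40 = 1.30 before any drop-out, so even a single pooled percentage refers to no defined period.

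If the columns are lead-in arms and the synopsis definitions apply, the imbalance has a direction. Lead-in placebo patients who are assigned a track are planned for 52 weeks, and the active column is a blend of 40 and 52. A higher percentage in the placebo column could then be taken for an effect of no prior exposure when part of it is extra observation. The comparison is a natural one, since SAP 9.1.1 contrasts the same two groups for efficacy.

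**Working it through.** **The plan's own figure.** Protocol 6.1 and SAP Section 3 give a maximum of about 64 weeks of continuous treatment. Lead-in 12 + P303 12 + Track A 40 = 64, which reproduces it.

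**Inputs.** From the documents: 40 and 52 weeks. Assumed, because the documents give none: event risk, hazard shape, drop-out, and the share *a* of the lead-in active column that is Track A. The placebo column is taken as all Track B, following the synopsis.

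**Constant hazard, no drop-out.** p52 = 1 − (1 − p40)^(52/40), and the column gap is *a* × (p52 − p40).

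| Risk at 40 weeks | Risk at 52 weeks | Gap between tracks | Column gap, a = 50% | Column gap, a = 75% |
|---|---|---|---|---|
| 5% | 6.5% | 1.5 | 0.7 | 1.1 |
| 10% | 12.8% | 2.8 | 1.4 | 2.1 |
| 20% | 25.2% | 5.2 | 2.6 | 3.9 |
| 30% | 37.1% | 7.1 | 3.6 | 5.3 |
| 50% | 59.4% | 9.4 | 4.7 | 7.0 |

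Gaps are in percentage points. In a pooled column with the same hazard throughout, the 20% row can read anywhere from 20.0% to 25.2%, depending only on the track mix.

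**Sensitivity of the 5.2-point track gap in the 20% row:**
- Hazard after Week 12 half the earlier hazard: 4.0 points. One quarter: 2.8. No events after Week 12: 0.
- Constant hazard with exponential drop-out of 20% by Week 40: 4.0 points (18.0% and 22.0%). With 40%: 2.9.
- Same track mix in both columns: the column gap is 0.

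**A combined case.** Take 30% risk, 30% drop-out by Week 40 and *a* = 70%. Crude shares are 25.5% at 40 weeks and 30.2% at 52. The active column is 0.7 × 25.5 + 0.3 × 30.2 = 26.9%, and the gap is 3.3 points.

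**What a rate does.**
- With constant hazard and 20% at 40 weeks, the weekly hazard is −ln(0.8)/40 = 0.00558. Over 52.18 weeks this is 29.1 first events per 100 patient-years on both tracks, and the artefact disappears.
- Suppose instead that 20% have a first event by Week 12 at constant hazard, and none later. Crude percentages are 20% on both tracks. Mean time at risk is 0.2/0.0186 = 10.8 weeks up to Week 12, plus 0.8 × 28 = 22.4 on Track A or 0.8 × 40 = 32 on Track B. The rates are 31.5 and 24.4 per 100 patient-years.

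A rate on its own can therefore create a difference where there is none, and a common cut-off is needed beside it.

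**The case against.** **Columns by arm are an inference.** Sections 10.1 to 10.1.2 do not mention treatment group, whereas the disposition, deviation, baseline and C-SSRS sections do. The rule in 7.1 is qualified as general, and the protocol plans a single group. This stands: a between-column artefact exists only if the tables are by arm. It does not help the pooled column.

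**The track-by-arm link rests on one of two definitions.** SAP Section 3 carries no arm condition. Inclusion criterion 1 admits P303 completers from either arm, and those who had placebo fit neither track as the synopsis words them. SAP 3.2 also says that patients and site staff will not know the lead-in treatment, so it is unclear how sites would apply an arm-based track. This stands too. However, a zero gap needs the same track mix in both columns, and nothing in the plan ensures that.

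**A reader might infer that incidence differs between columns by design, by up to 9 points.** The documents do not support this. What may differ by design is planned time at risk; incidence differs only if first events arise in Weeks 40 to 52. The 9-point figure also needs a 50% risk and an active column made up wholly of Track A, whereas that column also holds 52-week patients.

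**SAP 12.2 already uses at-risk denominators.** It does, for oral-cavity events, all TEAEs and serious TEAEs, so it would be wrong to say that the SAP ignores time at risk. But pooling over three studies and timing from first active dose mean these tables cannot correct P306 columns. The overall summary in 12.2 is itself crude.

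**The gaps are small beside sampling error.** With an assumed 100 per column, the standard error of a difference near 30% is √(2 × 0.3 × 0.7/100) = 6.5 points. That is fair for a single term, but longer observation can only push percentages one way across all terms.

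**Conclusion.** The point holds as a limit on interpretation. On any reading, the P306 percentages in SAP 10.1 blend 40-week, 52-week and partial follow-up. On the reading that combines arm columns with the synopsis track definitions, planned time at risk also differs between columns, in the direction that raises the lead-in placebo column.

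For a 20% event the column gap is about 2.6 to 3.9 points under constant hazard, no drop-out and an assumed 50% to 75% of the active column on Track A. It is smaller with drop-out or front-loaded events, and zero with equal track mix. No between-arm AE test is planned, so no error rate is affected. The change is worth making because it is cheap and bears on the primary objective, but the tables are not invalid without it.

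**What to change.** Keep the crude percentages in SAP 10.1. For any NEAE, serious NEAEs, NEAEs leading to discontinuation, each oral-cavity category and common preferred terms, add:

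- **(a)** incidence through Week 40 for all participants, with Weeks 40 to 52 shown separately for Track B among those still on treatment at Week 40;
- **(b)** patients with a first event per 100 patient-years at risk, from first P306 dose to first event or else last dose, with exact Poisson 95% confidence intervals, overall and per column if columns are by arm.

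Add the rate in (b), on that section's own exposure period, to the overall summary in SAP 12.2. State whether the AE tables are pooled or by lead-in arm, and give track-by-arm counts. Reconcile the track definitions in the protocol synopsis and SAP Section 3, including where P303 completers who had placebo belong.

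Cost: SAP wording and some extra output. AE onset is recorded (protocol 10.4.1) and dose dates are already used for exposure (SAP 11.2). A rule for partial AE onset dates should be stated, since those in SAP 7.3.1 are written for medication dates. The rate assumes a roughly constant hazard, which (a) lets the reader check.
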